### 9.6.2 External Investigative Site Sample Preparation and Shipment:

Once fresh samples (blood and bone marrow aspirate) are collected, the vacutainers will be refrigerated and stored per instructions below. There is no required processing for any of the samples by the participating site prior to shipment.

1. Package tubes at room temperature and wrap in a liberal amount of paper towel around the tubes to ensure adequate insulation of the specimen(s) and absorption in the event of a breakage.
2. Place wrapped specimen in a biohazard labeled Ziploc bag or sealable bag with a fridge pack and securely close.
3. Wrap bubble wrap around the bag and place in a cardboard box. If space remains in the box, stuff with extra paper towel to reduce shifting of samples.
4. Complete the shipping requisition form using the address listed below. Prepare the package for shipping, applying packing tape as needed.
5. Ship the package using FedEx or UPS next day or overnight delivery the same day the sample was collected.
6. Only ship Monday-Thursday and avoid shipping before a holiday as the lab does not receive packages on Saturday or on holidays.
7. With each shipment, please include the following:
  - a. An inventory sheet including a complete list of samples shipped (patient number, timepoint, study #) must accompany each shipment. Please sign and date the form and retain a copy for site record maintenance. **A sample requisition form will be provided by the lead site for use in sample shipment inventory.**

CONFIDENTIAL

This document is confidential. Do not disclose or use except as authorized.

- b.** An electronic copy (Word or pdf) of the sample requisition must also be sent via email and include the tracking number of the package. The listing must also include a contact name, address and phone number of the person who is responsible for the shipment.
- 8. Please email the Lead Site Research Project Manager to notify of an incoming shipment at least 48 hours prior to a shipment
- 9. Samples may be shipped **via overnight air to:**

[name], Principal Research Technician  
CLL Center, [name] lab  
Dana Farber Cancer Institute  
[name]  
Boston, MA 02115, U.S.A.  
[contact] (phone)

Please retain a copy of both the Fed-Ex or UPS tracking number, and of the completed requisition form for each sample sent.

CONFIDENTIAL

This document is confidential. Do not disclose or use except as authorized.

## 10. STUDY CALENDAR

Baseline evaluations are to be conducted within 4 weeks (28 days) prior to patient registration with the exception of the required bone marrow biopsy, which can be done within 12 weeks (90 days) prior to registration if no significant intervening treatment has occurred since the biopsy. Treatment should begin as soon as possible after registration. In the event that the participant's condition is deteriorating, laboratory evaluations should be repeated within 48 hours prior to initiation of the next cycle of therapy.

Assessments and correlative lab draws must be performed prior to administration of any study agent. Study assessments and agents should be administered within +/- 3 days of the protocol-specified date during the dose ramp up period, +/- 7 days during the rest of the combination portion, and +/- 14 days after the completion of the combination portion (Cycle 12), unless otherwise noted.

For venetoclax ramp-up instructions, please refer to section [5.1.2](#).

If after at least one year of treatment, a patient achieves a complete remission (CR) or complete remission with incomplete count recovery (CRi) with MRD-negativity in the peripheral blood and bone marrow, they will have the option to discontinue venetoclax in favor of active disease monitoring in follow up. If after at least two years of treatment (Cycle 25 restage), a participant achieves a partial remission (PR) with MRD-negativity in the bone marrow, they will have the option to discontinue venetoclax in favor of active disease monitoring.

In the event that the participants who have discontinued treatment in favor of disease monitoring have recurrent disease as defined by MRD testing ( $>10^{-4}$ ) in at least two MRD assessments they can restart venetoclax. Patients will be treated with a dose ramp up as per the label, starting with 20 mg daily and escalating to 400 mg daily. Prophylaxis against and treatment of TLS will be performed as during initiation of venetoclax therapy. If patients do not achieve MRD negativity after reaching full dose venetoclax monotherapy, they have the option to add duvelisib at the highest dose they previously tolerated and continue it until MRD negativity is achieved on two successive peripheral blood MRD assessments or indefinitely depending on tolerability.

CONFIDENTIAL

This document is confidential. Do not disclose or use except as authorized.

**Table 9: Study Calendar:**

Cycle = 28 days (except for cycle 1 which will vary in length)	Screening**	Cycle 1 (+3 Days)					Cycle 2 (+7 Days)				Cycles 3-6 (+7 Days)	Cycles 7+ ( 2 cycles +/- 7d until C13, then q3 cycles +/-14d through cycle 60, then q6 months +/- 14 days	End of Treatment 	Active Follow Up (q3 months +/- 14 days ) and Disease Monitoring 	Survival Status	
		Day 1 	Day 2	Day 8 	Day 15 	Day 22 Day 29 Day 36 Day 43	Day 1	Day 8	Day 15	Day 22						Day 1
Procedure / Days	-28-0	Day 1 	Day 2	Day 8 	Day 15 	Day 22 Day 29 Day 36 Day 43	Day 1	Day 8	Day 15	Day 22	Day 1	Day 1				
Informed consent	X															
Duvelisib		X	X	X	X	X	X	X	X	X	X	X (through cycle 12)				
Venetoclax				X	X	X	X	X	X	X	X	X				
Survival Status																X
PK assessments (phase I study only)		X	X	X	X	X										
History and Physical Exam + Vital signs 	X	X		X	X	X	X	X	X	X	X	X	X	X	X	
Serum pregnancy test	X*															
Physical Exam Lymph node measurements		X 		X 												
Quality of life survey (appendix F)		X		X												
Concurrent Medications	X	X		X	X	X	X	X	X	X	X	X	X	X		
Urinalysis	X															
BM aspirate/biopsy 	X 										X	X	X	X		
SPEP + Immunoglobulins 	X										X	X				

CONFIDENTIAL

This document is confidential. Do not disclose or use except as authorized.

Cycle = 28 days (except for cycle 1 which will vary in length)	Screening**	Cycle 1 (+3 Days)					Cycle 2 (+7 Days)				Cycles 3-6 (+7 Days)	Cycles 7+ ( 2 cycles +/- 7d until C13, then q3 cycles +/-14d through cycle 60, then q6 months +/- 14 days	End of Treatment 	Active Follow Up (q3 months +/- 14 days ) and Disease Monitoring 	Survival Status
		Day 1 	Day 2	Day 8 	Day 15 	Day 22 Day 29 Day 36 Day 43	Day 1	Day 8	Day 15	Day 22					
Procedure / Days	-28-0	Day 1 	Day 2	Day 8 	Day 15 	Day 22 Day 29 Day 36 Day 43	Day 1	Day 8	Day 15	Day 22	Day 1	Day 1			
ECOG performance status	X						X				X	X	X	X	
EKG	X 														
Serology: SARS CoV2-,HIV, HCV, HBV 	X														
CT or PET/CT scan and Response Assessment 	X										X	X	X	X	
Hematology (CBC with differential and platelets)	X	X		X	X	X	X	X	X	X	X	X	X	X	
Serum Chemistry (CMP, magnesium, uric acid, phosphate, LDH, amylase and lipase) 	X	X		X	X	X	X	X	X	X	X	X	X	X	
CMV viral load 	X						X				X	X			
PT/PTT/INR	X														
FISH, TP53, NOTCH1, SF3B1, and IGHV testing 	X														
Correlative studies**	X 	X 		X			X				X	X	X	X	
Adverse Event Evaluation	X	X		X	X	X	X	X	X	X	X	X	X	X	
MRD assessment 											X	X	X	X	

 During cycle 1, patients will start with duvelisib alone on days 1-7. Dose ramp up of venetoclax will begin on C1D8. Please refer to section 5.1.2 for admission requirement, TLS monitoring, and inpatient versus outpatient dosing of venetoclax and ramp up instructions.

CONFIDENTIAL

This document is confidential. Do not disclose or use except as authorized.

-  C1D8 patients will initiate venetoclax ramp up and continue duvelisib
-  Please refer to section 5 for venetoclax ramp-up dosing per arm.
-  Unilateral bone marrow aspirate and/or biopsy required within 12 weeks (90 days) prior to C1D1.
-  Bone marrow biopsy and aspirate will be mandatory at study entry and at C7D1 (+7 days), C13D1 (+7 days), and C25D1 (+14 days). Bone marrow biopsies will be at the discretion of the treating investigator thereafter. MRD will be tested in the bone marrow each time a standard of care or clinically indicated biopsy is performed both during venetoclax maintenance and during active follow up through the Mayo Clinic Lab. Please refer to Section 9 and Table 10 for additional details on schedule and ordering instructions.
-  Marrow sample requested for correlative studies if bone marrow is done as standard of care, or part of protocol schedule.
-  SPEP required at baseline and then at Cycles 3, 6, 9, 13 and every 3 cycles thereafter only if M protein detected at baseline; If no M protein detected at baseline, IgG, IgA, IgM to be checked Cycles 3, 6, 9, 13 and every 3 cycles thereafter (B2M only at baseline, C6 and C13).
-  C4D1, C7D1, and C13D1 (+/- 7 days for each). De-identified scans (Initials, assigned patient number, study number, date of scan, and timepoint must be included) will be sent to the DFCI/Lead site project manager to then send for analysis by the Tumor Imaging Metrics Core- Scans may also be uploaded to the TIMC portal by local radiology
-  After Cycle 13, CT (Chest, Neck, Abdomen and Pelvis) or PET/CT (Richter's Patients) scans may occur just prior to every 6 cycles (+/- 14 days), or per investigator discretion. De-identified scans (Initials, assigned patient number, study number, date of scan, and timepoint must be included) will be sent to the DFCI/Lead site project manager to then send for analysis by the Tumor Imaging Metrics Core- Scans may also be uploaded to the TIMC portal by local radiology- For instructions on sending scans to Dana-Farber for central review, please refer to [section 11.1.3](#)
-  FISH for both CLL/SLL are to be done locally- *IGHV*, *TP53* testing can be performed locally or externally via Mayo Clinic Laboratories; If ordering through Mayo Clinic Laboratories, please refer to section 9 and table 10. – *SF3B1* and *NOTCH1* to be ordered for DFCI patients only.
-  CMV viral load testing should be performed at the time of screening and monthly thereafter in patients while on duvelisib. Local testing is permitted.
-  End of treatment visit should occur at the next study visit following a completed cycle after study drug was administered and include adverse event monitoring for 30 days following drug discontinuation (visit window +/-14 days). End of treatment due to MRD-CR or MRD- PR does not require labs or exam to be repeated after the C13 or C25 restaging unless clinically indicated.
-  Baseline correlative studies may be obtained either at the screening visit or prior to study drug administration on C1D1.  
\* Within 3 days of Cycle 1 Day 1  
\*\* Please see section [5.2](#) for requirements for treatment and Table 10 for full correlative and send out sample collection schedule
-  MRD will be evaluated in the bone marrow prior to cycle 7, 13, and 25 (+/-7 days) and any time a clinically indicated bone marrow procedure is done thereafter- MRD assessments will also be performed in the peripheral blood prior to cycle 4, 7, 11, 13, 16, 19, 22, 25 and every three cycles up to Cycle 60, then every 6 cycles thereafter- MRD of the blood will be assessed every 3 months or every 6 months at minimum during follow up/active disease monitoring. Please refer to [section 9](#) and [Table 10](#) for directions on ordering, collection, and shipping of samples to Mayo Clinic Laboratories
-  Amylase and lipase required only while on duvelisib
-  Please refer to section [5.6](#) for more specific follow up and active disease monitoring requirements
-  Includes history and physical exam (with standard review of systems) in addition to blood pressure, pulse rate, and temperature- On Cycle 1 Day 1 and Cycle 1 Day 8, the physical exam will also include measurement and assessments of palpable lymph nodes
-  Local EKG machine; single test
-  Participants will be followed for survival status indefinitely after active follow up unless they have withdrawn consent, died, or are lost to follow up
-  SARS- COV2, Hepatitis B ,C, and HIV serologies: HBV surface antigen, HBV surface antibody, HBV core antibody: if HBV core antibody is positive, must have a negative HBV viral load to enroll. HCV antibody: if positive, must have negative HCV viral load to enroll. HIV 1/2 antibody: must have negative result to enroll. SARS-COV2 must have negative PCR to enroll.

CONFIDENTIAL

This document is confidential. Do not disclose or use except as authorized.

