### **3.2 Exclusion Criteria**

3.2.1 Previous treatment with venetoclax or duvelisib (prior venetoclax allowed for RS patients and for CLL/SLL patients if they have been off venetoclax therapy for at least one year prior to enrollment)

3.2.2 Patients receiving cancer therapy (i.e., chemotherapy, radiation therapy, immunotherapy, biologic therapy, surgery within 2 weeks of Cycle 1/Day 1 with the following exceptions:

- For patients on targeted therapies, a washout of least five half-lives is required
- Patients who experience clinical deterioration may start therapy after a shorter washout period with prior approval by the PI
- Corticosteroid therapy (prednisone or equivalent  $\leq 20$  mg daily) is allowed

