### 9.1 BH3 Profiling:

BH3 profiling is a functional assay that detects the proximity of cells to the threshold of apoptosis (i.e. priming) through interrogation of BCL-2 family members. To perform a BH3 profile, we add individual peptides, which bind to the BH3-only region of anti-apoptotic proteins, to gently permeabilized malignant cells. We then use Fluorescence-activated cell sorting (FACS) to measure the amount of mitochondrial depolarization induced by each peptide, as measured by cytochrome c release. Previous trials at our institution have suggested that this technique may be useful as an effective predictor of response in CLL.

We hypothesize that patients whose cells undergo significant depolarization to the BIM BH3 peptide (primed) will have superior clinical response to duvelisib plus venetoclax as compared to patients whose cells undergo minimal BIM BH3 depolarization (unprimed). These assessments will be made on circulating CLL cells from the peripheral blood drawn from patients at baseline and after three and six months of combination therapy.

If we have bone marrow aspirates available, we will also perform BH3 profiling to see whether the level of priming in CLL cells from these tissues is a better predictor of response than peripheral blood CLL cells.

After 1 week of duvelisib monotherapy on cycle 1 day 8 (prior to receiving venetoclax), we will obtain another peripheral blood sample. We will compare the BH3 profile of this steady-state sample to a baseline sample, which will allow us to assess the short term change in apoptotic priming induced by in vivo duvelisib as a single agent.

Lastly, peripheral blood will be collected from subjects at the time of disease progression, and the BH3 profile of these samples will be compared to subjects' baseline. By measuring the cytochrome c loss in response to other BH3 peptides, such as BAD, MS-1 and HRK, it will be possible to determine whether dependencies on anti-apoptotic proteins other than BCL-2 predicts

CONFIDENTIAL

This document is confidential. Do not disclose or use except as authorized.

resistance to therapy. We can also determine whether BCL-2 dependency predicts response to therapy or risk of tumor lysis syndrome.

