**Table 10: Correlative and Required Send out Sample Schedule:**

Sample Time Point	Container 	Sample Type	Shipping Method	Recipient
Baseline or C1D1 Predose	6x6mL Green 1x6ml Red	Peripheral Blood	Hand-delivered or Fridge pack overnight shipping	Brown Lab
	1x6ml Green	Bone Marrow Aspirate	Hand-delivered or Fridge pack overnight shipping	Brown Lab
	MUTATIONS	Peripheral Blood	Ambient	Mayo Clinic or Local Assay
	1x Oragene Kit	Saliva 	Ambient	Brown Lab
C1D8 Predose	6x6mL Green 1x6ml Red	Peripheral Blood	Hand-delivered or Fridge pack overnight shipping	Brown Lab
C2D1	6x6mL Green 1x6ml Red	Peripheral Blood	Hand-delivered or Fridge pack overnight shipping	Brown Lab
C4D1	1x6ml Lavender	Peripheral Blood	Ambient	Mayo Clinic MRD
	6x6mL Green 1x6ml Red	Peripheral Blood	Hand-delivered or Fridge pack overnight shipping	Brown Lab
C7D1, C13D1, C25D1	6x6mL Green 1x6ml Red	Peripheral Blood	Hand-delivered or Fridge pack overnight shipping	Brown Lab
	1x6ml Green	Bone marrow Aspirate		
	1x6ml Lavender	Bone marrow Aspirate	Ambient	Mayo Clinic MRD
	1x6ml Lavender	Peripheral Blood	Ambient	Mayo Clinic MRD

CONFIDENTIAL

This document is confidential. Do not disclose or use except as authorized.

C11D1	1x6ml Lavender	Peripheral Blood	Ambient	Mayo Clinic MRD
C16D1	1x6ml Lavender	Peripheral Blood	Ambient	Mayo Clinic MRD
C19D1	6x6mL Green 1x6ml Red	Peripheral Blood	Hand-delivered or Fridge pack overnight shipping	Brown Lab
Clinically Indicated	1x6ml Green	Bone marrow Aspirate	Hand-delivered or Fridge pack overnight shipping	Brown Lab
	1x6mL Lavender	Bone Marrow Aspirate	Ambient	Mayo Clinic MRD
Confirmation of Complete Response	6x 6mL Green 1x6ml Red	Peripheral Blood	Hand-delivered or Fridge pack overnight shipping	Brown Lab
	1x6ml Green 	Bone Marrow Aspirate	Hand-delivered or Fridge pack overnight shipping	Brown Lab
	1x6mL Lavender 	Bone Marrow Aspirate	Ambient	Mayo Clinic MRD
	1x6ml Lavender	Peripheral Blood	Ambient	Mayo Clinic MRD
End of Treatment or Suspected Progression  OR  Prior to Resuming Venetoclax after Discontinuation	6x6mL Green 1x6ml Red	Peripheral Blood	Hand-delivered or Fridge pack overnight shipping	Brown Lab
	1x6ml Green	Bone Marrow Aspirate	Hand-delivered or Fridge pack overnight shipping	Brown Lab

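### Baseline blood for BH3 profiling and CyTOF may be drawn at screening, before prior-therapy washout is complete, so for some patients the one-week change cannot be credited to duvelisib alone

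*Combined protocol and SAP*

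**What the plan says.** **Timing of the sample.** Footnote 13 to Table 9 states: "Baseline correlative studies may be obtained either at the screening visit or prior to study drug administration on C1D1". Table 10 repeats the choice in its first row, "Baseline or C1D1 Predose". The one timing condition, in Section 10, is "Assessments and correlative lab draws must be performed prior to administration of any study agent". The screening column of Table 9 runs from Day -28 to 0, and the text of Section 10 counts from registration: "Baseline evaluations are to be conducted within 4 weeks (28 days) prior to patient registration".

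**Washout.** Section 3.2.2 excludes patients on cancer therapy, in a list that ends "surgery within 2 weeks of Cycle 1/Day 1 with the following exceptions". Two of the exceptions matter here: "For patients on targeted therapies, a washout of least five half-lives is required" and "Patients who experience clinical deterioration may start therapy after a shorter washout period with prior approval by the PI". None of this refers to the correlative sample.

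**Use of the sample.** Section 9.1 compares the C1D8 BH3 profile with a baseline sample, "which will allow us to assess the short term change in apoptotic priming induced by in vivo duvelisib as a single agent". Sections 2.7 and 9.2 compare CyTOF subsets between time points with a paired Wilcoxon test. Section 13.3 relates the change in priming from baseline to duvelisib monotherapy to overall response.

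**The concern.** There is no control arm, so the pre-dose sample is the only reference for what one week of duvelisib does to priming, BCL-2 dependency and immune subsets. That reference needs to be a sample free of other active drugs, taken close to the first dose. The plan requires neither.

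The situation can arise in this population. Section 3.1.2 admits CLL/SLL patients who progressed during a previous therapy. Section 3.2.1 restricts prior venetoclax and duvelisib only, so a patient coming off another PI3K inhibitor is not excluded. By the protocol's own account such a drug is not neutral: Section 2.5 says PI3K inhibition shifts the apoptotic threshold and sensitivity to BCL-2 inhibition, and Section 2.7 says PI3K inhibitors alter immune subsets. For such a patient the measured change runs from the previous drug to duvelisib, not from no drug to duvelisib.

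At stake is the single-agent reading of the standard BH3 and CyTOF one-week changes, and the exploratory associations built on them.

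**Working it through.** The plan gives no sample size, power or test level for the one-week change, so there is no planned figure to reproduce. The check is day arithmetic and a comparison of the rules.

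**1. Interval from baseline to C1D8.**
- C1D1 pre-dose draw: 8 - 1 = 7 days, subject to the 3-day visit window during ramp-up.
- Day -28 draw: 28 + 7 = about 35 days. It could be somewhat longer, because Section 10 counts the 28 days back from registration and treatment starts after that.

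**2. Time on the previous drug that the rules permit after a Day -28 draw.**
- Two-week rule: 28 - 14 = 14 further days. A sample from the first half of the window can be fully on treatment.
- Five-half-life rule, using the only suitable half-life in the protocol (venetoclax, 17 to 41 hours, Section 8.2.1): 5 x 17 / 24 = 3.5 days and 5 x 41 / 24 = 8.5 days, leaving 28 - 8.5 = 19.5 to 28 - 3.5 = 24.5 further days. This shows how the rule works. It could apply only to Richter's patients, since CLL/SLL patients must have been off venetoclax for at least a year.

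**3. Does another provision close the gap?** No section requires washout before the baseline correlative draw, says which sample is the paired baseline when both exist, or adjusts for prior therapy or sample date. The other two one-week measures, node size and quality of life, are fixed at C1D1 and C1D8. Only the laboratory markers float.

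**4. Size.** If a share q of pairs carries a withdrawal shift of s (in SDs of the paired change), the mean change is biased by q x s. The documents give neither. Purely as an illustration, I assumed no true duvelisib effect, all shifts in one direction, and a paired Wilcoxon test at two-sided 0.05 with 3,000 simulated trials. The sample sizes are the first-stage and total CLL/SLL numbers.

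| q | s | Bias (SD) | False positives, n = 12 | False positives, n = 35 |
|---|---|---|---|---|
| 0 | - | 0 | 0.04 | 0.05 to 0.06 |
| 0.25 | 0.5 | 0.125 | 0.05 | 0.10 |
| 0.25 | 1.0 | 0.25 | 0.09 | 0.24 |
| 0.5 | 0.5 | 0.25 | 0.11 | 0.29 |
| 0.5 | 1.0 | 0.5 | 0.25 | 0.72 |

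The range runs from negligible to severe and depends wholly on q and s. If the shift opposes duvelisib's effect, the result is attenuation instead.

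**The case against.** **Only exploratory work is affected.** Section 9 calls the correlative results supportive and lets the principal investigator drop collections or analyses. The complete response endpoint, dose-limiting toxicity, the two-stage rule, the Richter's rule and toxicity stopping do not use these samples. This stands and limits the weight of the point.

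**The problem needs three things at once:** a screening draw, incomplete washout at that draw, and a drug that moves the marker. Patients long off therapy, or sampled at C1D1, are largely unaffected. This stands.

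**There is a partial cross-check.** Dynamic BH3 profiling exposes cells to duvelisib outside the body, so it does not depend on the interval to C1D8. That helps for BH3 but not for CyTOF.

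**Existing records might support a sensitivity analysis.** Concurrent medications are recorded at screening and C1D1, and external shipments carry an inventory showing the time point. That may be workable, but no such analysis is planned.

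**A fixed C1D1 draw has a price.** External sites ship only Monday to Thursday and avoid days before holidays. The blood set is 7 x 6 = 42 mL, and in phase I C1D1 is also a serial pharmacokinetic day. The shipping limit already applies to C1D8, without which there is no pair, and C1D1 is already a permitted correlative draw. Some loss of samples remains possible, so a back-up is sensible.

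**Conclusion.** The gap is real and limited. For patients sampled at screening while on, or not yet washed out of, a prior agent that moves these markers, the attribution in Section 9.1 to duvelisib alone is not supported, and the interval can be about 35 days instead of about 7. The conclusion rests on the timing rules as written and on the protocol's own statements about PI3K inhibitors. Correcting it is a cheap improvement, not a condition for the trial's main conclusions.

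A reader might infer more than the documents support:
- **A stated percentage of attenuation.** Any such figure only restates an assumed share of affected patients. Share, size and direction are all unknown.
- **An error linked to outcome**, because deteriorating patients may have the shortest washout. The documents give no data connecting washout, sample timing and response.
- **Bias from every kind of prior therapy.** Sections 2.5 and 2.7 speak of PI3K inhibitors, not chemotherapy or immunotherapy in general.
- **A complete cure from moving the draw to C1D1.** Patients with an approved shortened washout may still not be clear on that day.

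**What to change.** No change to the washout rule is needed or proposed. The changes concern sampling and analysis.

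1. In footnote 13 and Table 10, name the C1D1 pre-dose peripheral blood as the paired baseline for BH3 profiling and CyTOF. Keep the screening option for marrow, saliva and mutation samples, and as a back-up when C1D1 blood cannot be shipped or fails.
2. Record the sample date and the date of last prior therapy for every baseline sample.
3. State in Section 13.3 that any pair whose baseline preceded completed washout will be excluded from the baseline-to-C1D8 change or examined in a sensitivity analysis. Include patients with an approved shortened washout and those already enrolled with only a screening sample.

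**Cost:** wording changes and two dates. C1D1 already has a scheduled blood draw, so no visit is added. The downside is that some C1D1 samples may be lost to the Monday-to-Thursday shipping limit. Baselines already collected cannot be redrawn and can be handled only through step 3.
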